8.1.2 Baseline seizure burden

Baseline seizure burden is defined as seizure burden measured on the continuous VEEG (total ENS in minutes per hour) during a period of up to 1 hour immediately prior to the first administration of study medication.

8.1.2.1 Baseline non-severe seizure burden

Baseline non-severe seizure burden is defined as seizure activity (total ENS duration in minutes) for \leq 15 minutes in all of the following 30-minute time periods: 0-30 and >30-60 minutes during the 1-hour Baseline Period. For example, if total ENS duration of 18 minutes occurred as 9 minutes of ENS duration in each of any two 30-minute time periods or 18 minutes of ENS are distributed over several 30 minute time intervals so that the ENS duration in each interval is \leq 15 minutes, then the baseline seizure burden is non-severe.

8.1.2.2 Baseline severe seizure burden

Baseline severe seizure burden is defined as seizure activity (total ENS duration in minutes) for >15 minutes in at least one of the following 30-minute time periods 0-30 and >30-60 minutes during the up to 1-hour Baseline Period. For example, if total ENS duration is 18 minutes and the distribution of ENS duration is 16 minutes in 0-30 minutes time period and 2 minutes in >30-60 minutes time period, then the baseline seizure burden is severe.

8.1.3 ENS definition

For this study, an ENS is defined as an electroencephalographic (EEG) seizure lasting for at least 10 seconds on VEEG.

8.1.4 Average per hour seizure burden (ENS in minutes per hour)

Average per hour seizure burden per subject (ENS in minutes per hour) is defined as total seizure burden measured over a period of time (in minutes) divided by the number of hours in the given period of time. That is all seizure activity times (durations in minutes) will be added up across the Evaluation Period. It will then be divided by the total duration of the Evaluation Period to calculate a seizure burden value in minutes per hour. Average seizure burden value will be calculated during the Baseline period and the Evaluation Period (and transformed the data by taking log (x +1) for both Baseline and the Evaluation Period if needed).

8.1.5 Percent change in baseline seizure burden

Percent change in baseline seizure burden is defined as a difference between average per hour seizure burden at baseline (calculated over the 1-hour baseline period) and average per hour

seizure burden calculated over given period of time after the start of initial BRV treatment divided by the average per hour seizure burden at baseline and multiplied by 100.

If the percent change is $\geq 80\%$ (reduction in baseline) and baseline seizure burden is non-severe or if the percent change $\geq 50\%$ (reduction in baseline) and baseline seizure burden is severe then this subject is defined as **BRV responder**. No rounding will be applied, one decimal will be considered for comparison (for example, if the percent change is 79.999%, then consider 1 decimal as 79.9% which is less than 80%).

8.1.6 Responder to other treatment

Responder to other treatment is defined as subject who stopped BRV or switched from BRV to act as a rescue medication and achieved at least 80% reduction (≥ 80 percent change) in non-severe seizure burden from start of other treatment to end of other treatment or at least 50% reduction (≥ 50 percent change) in severe seizure burden measured from initiation of other treatment to end of other treatment during the 96-hour Evaluation Period. Baseline Period for other treatment is defined as 1 hour prior to starting the other treatment. Other treatment Evaluation Period is from the start to the end of other treatment or to the end of 96-hour Evaluation Period if other treatment end is after the 96-hour Evaluation Period.

8.2 Statistical analysis of the secondary efficacy variable

8.2.1 Derivations of the main secondary efficacy variable

The main secondary efficacy variable is the proportion of responders to BRV treatment from Baseline to 3 hours after the initial BRV dose. The numerator is the number of BRV responders for main secondary efficacy variable defined in [Section 8.1](#). The denominator is defined as the number of the subjects in the FAS from Confirmatory Cohorts.

8.2.2 Analysis of the main secondary efficacy variable

The main secondary efficacy variable will be summarized using descriptive statistics (counts and proportions with the 95% CIs). See [Section 3.1](#) for the details. Subgroup analysis of main secondary efficacy variable will be produced for the latest primary cause of seizure (see categories in [Section 4.8](#)) and concomitant use of hypothermia. Listing of main secondary efficacy variable will be provided.

To further evaluate BRV efficacy, a descriptive comparison will be conducted of the main secondary efficacy variable data from N01349 with published responder rates for MDZ (historical control group matched in age and condition) effective for the treatment of neonatal seizures in subjects of similar age (<29 days of postnatal age) and condition (neonatal seizures as noted in N01349 eligibility criteria). A recent study (Weeke et al, 2016) provides response rates for second line MDZ treatment of neonatal seizures in a similar population and with primary endpoints comparable to N01349. Results from this study, as well as results from other studies available in the literature at the time of N01349 completion and with populations and efficacy endpoints comparable to N01349, will be used for these descriptive comparisons.

A listing of main secondary efficacy variable will be provided for the FAS.

8.2.3 Sensitivity analysis of the main secondary efficacy variable

The impact of missing data on the assessment of the main secondary efficacy variable will be evaluated with sensitivity analyses. Subjects who drop out for reasons other than due to lack of

BRV efficacy, are switched over to another AED treatment, or are administered any rescue medication (including BZDs) will be excluded from the analysis.

The numerator of the main secondary efficacy variable is defined as the number of responders to BRV treatment from Baseline to 3 hours after the initial BRV dose (see [Section 8.1](#) for the definition of BRV responders). Subjects, who dropped out for reasons other than due to lack of BRV efficacy, are switched over to another AED treatment or received any rescue medication during the first 3 hours after the initiation of BRV treatment will be excluded from the analysis.

The denominator is defined as the number of the FAS subjects in the Confirmatory Cohorts with the following subjects excluded: subjects who dropped out for reasons other than due to the lack of BRV efficacy reasons, are switched to another AED or received any rescue medication (including BZDs) during the first 3 hours after the initiation of BRV treatment.

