13.7 Handling of dropouts or missing data

For subjects who dropped out during the Evaluation Period, the number of hours from the start of the Evaluation Period to the time of withdrawal (in hours) will be considered for analysis. Subjects in the Confirmatory Cohorts who started another AED, increased the dose or frequency of administration of an AED ongoing at the time the first BRV infusion started, or are switched to another AED, or have been administered any rescue medication for the treatment of ENS during the first 3 hours after initiation of BRV treatment will be considered BRV nonresponders.

The impact of missing data on the assessment of the main secondary efficacy variable will be evaluated with sensitivity analyses with further details to be included in the SAP.

No imputation of missing values associated with an individual date or visit is planned for the safety analysis, with the exception of partial date information for AEs and concomitant medications, in order to determine whether they are treatment emergent.

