8.1 Endpoint definitions and derivations

8.1.1 BRV responder and non-responder definitions

A BRV responder is defined as a subject who achieves the following reduction in seizure burden (ENS in minutes per hour) without need for rescue medication, compared to the seizure burden measured during the Baseline Period immediately prior to BRV administration, evaluated for a 2-hour period starting 1 hour after the start of initial BRV treatment:

- At least 80% reduction (≥ 80 percent change) in non-severe seizure burden
(Non-severe seizure burden is defined as $\leq 50\%$ seizure activity on video-electroencephalography (VEEG) in all 30-minute timespans)

OR

- At least 50% reduction (≥ 50 percent change) in severe seizure burden

(Severe seizure burden is defined as >50% seizure activity on VEEG in any 30-minute timespan. Timespans of 30 minutes refer to the following intervals within the 2-hour period: 0 to \leq 30 minutes, >30 to \leq 60 minutes, >60 to \leq 90 minutes, and >90 to \leq 120 minutes.)

Subjects not meeting the BRV responder definition are classified as BRV non-responders. In addition, subjects who drop out due to lack of BRV efficacy, are switched over to another AED treatment, or are administered any rescue medication (any treatment initiation with a new AED, or any increase of dose or frequency of an existing concomitant AED for the treatment of seizures during the Evaluation Period - including BZDs) during the first 3 hours after initiation of BRV treatment will be considered BRV non-responders.

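### SAP 8.2.3 is presented as a missing-data sensitivity analysis, but it removes subjects rescued or switched in the first 3 hours, who are non-responders by rule, and leaves missing VEEG untested

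*SAP*

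**What the plan says.** Protocol 13.7 commits to the analysis: "The impact of missing data on the assessment of the main secondary efficacy variable will be evaluated with sensitivity analyses", with details left to the SAP. SAP 8.2.3 repeats that purpose and then defines the analysis by exclusion. "The denominator is defined as the number of the FAS subjects in the Confirmatory Cohorts with the following subjects excluded": first, "subjects who dropped out for reasons other than due to the lack of BRV efficacy reasons"; second, those who switched to another AED or "received any rescue medication (including BZDs) during the first 3 hours after the initiation of BRV treatment". The numerator paragraph removes the same groups. The opening paragraph of the section lists them without any time limit: subjects who drop out for reasons other than lack of "BRV efficacy, are switched over to another AED treatment, or are administered any rescue medication (including BZDs) will be excluded from the analysis".

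For the main analysis, SAP 8.1.1 lists "subjects who drop out due to lack of BRV efficacy, are switched over to another AED treatment, or are administered any rescue medication" and says that these events "during the first 3 hours after initiation of BRV treatment will be considered BRV non-responders". Protocol 10.1, 13.5.1 and 13.7 likewise make early rescue a non-response. The main denominator is every Confirmatory Cohort subject in the FAS (SAP 8.2.1). Entry to the FAS requires at least 2 hours of interpretable VEEG in the first 3 hours after the first dose (SAP 3.6.2). SAP 4.2 plans no imputation of efficacy data.

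**The concern.** A missing-data sensitivity analysis should vary what is assumed about subjects whose outcome is unknown. A baby rescued or switched within 3 hours has a known outcome under the plan's own rule: non-response. Deleting such babies conditions on not having failed. It changes the quantity being estimated, and it does not probe the missing data.

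The babies whose outcome really is unknown, because their VEEG is insufficient, never reach this analysis: it starts from the FAS, which has already left them out. The FAS also asks for 2 readable hours anywhere in the first 3, so a subject can be included with up to 1 hour of the 1-to-3-hour response window unreadable. SAP 8.2.3 has no rule for that case either.

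This is the only sensitivity analysis planned for the main efficacy variable. A reader who sees it beside the main result under a missing-data label could take a higher rate as evidence of robustness that the analysis cannot supply.

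**Working it through.** The documents give no expected responder rate, rescue rate or sensitivity result, so there is no stated figure to reproduce. All counts below are assumptions except N = 36, which is the planned minimum for the Confirmatory Cohorts (SAP 2.4), taken here as the FAS size. The documents name no CI method; exact (Clopper-Pearson) 95% intervals are used.

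**Notation.** R = responders among N; k = subjects rescued or switched in the first 3 hours; d = other excluded subjects; r = responders among those d.

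- Main rate = R/N
- SAP 8.2.3 rate = (R − r)/(N − k − d)

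**Step 1: the early rescue/switch deletion alone (d = 0).** These k subjects are all non-responders, so the numerator stays at R and only the denominator shrinks. The change is R/(N − k) − R/N = Rk/[N(N − k)]. This is never negative, and it is positive when both R and k are at least 1. An exhaustive check over all N up to 60 found no exception.

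| Responders | Removed (k) | Rate | Exact 95% CI |
|---|---|---|---|
| 12 | 0 | 12/36 = 33.3% | 18.6 to 51.0 |
| 12 | 2 | 12/34 = 35.3% | 19.7 to 53.5 |
| 12 | 5 | 12/31 = 38.7% | 21.8 to 57.8 |
| 12 | 10 | 12/26 = 46.2% | 26.6 to 66.6 |
| 18 | 0 | 18/36 = 50.0% | 32.9 to 67.1 |
| 18 | 6 | 18/30 = 60.0% | 40.6 to 77.3 |

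With 12 responders, the lower limit rises by 21.8 − 18.6 = 3.2 points for 5 removals and by 26.6 − 18.6 = 8.0 points for 10.

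**Step 2: the whole exclusion rule.** The rate falls only if the response proportion among everyone excluded exceeds the overall proportion, that is, if r/(k + d) > R/N. Two features of SAP 8.2.3 make this possible, again with R = 12 and N = 36:

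- Other-reason dropouts are excluded, and the non-responder rule in SAP 8.1.1 does not name them, so some may be responders. One such responder and no early rescue: 11/35 = 31.4%. Two early rescues and two such responders: 10/32 = 31.3%.
- The opening paragraph has no 3-hour limit. Read literally, it also removes 3-hour responders who were rescued or switched later. Six early rescues and four such responders: 8/26 = 30.8%.

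All three results are below 33.3%.

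**Step 3: what a missing-data analysis would show.** Assume 36 treated subjects, 12 known responders and m with undeterminable response. Early rescues stay in as non-responders. Counting the missing as non-responders gives 12/36 = 33.3% (18.6 to 51.0). Counting them as responders gives:

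- m = 2: 14/36 = 38.9% (23.1 to 56.5)
- m = 4: 16/36 = 44.4% (27.9 to 61.9)
- m = 6: 18/36 = 50.0% (32.9 to 67.1)

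The width of that range measures dependence on missing VEEG. SAP 8.2.3 produces nothing equivalent.

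**The case against.** Four arguments limit the point.

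First, a reader might infer that the analysis can only raise the responder rate. The documents do not support that. It holds for the early rescue/switch deletion, but Step 2 shows that the full rule can lower the rate. Nor is the analysis wholly unrelated to missing data: removing other-reason dropouts is a weak complete-case step.

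Second, a reader might infer that the shift in the lower confidence limit changes the efficacy conclusion. It does not. Protocol 13.5.1 compares the interval for the main variable, all Confirmatory Cohorts combined, with the historical rate, and SAP 8.2.1 keeps the full FAS denominator for that variable. In the 12/36 example the limit compared stays at 18.6%. SAP 4.5 adds that all analyses are descriptive and that no tests are done.

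Third, the shift may be small. The documents state no early rescue rate, they discourage rescue in the first 3 hours (Protocol 5.1.2 and 7.8.3), and Protocol 7.8.2 does not permit changes of concomitant seizure treatment in that window. Two removals move 33.3% only to 35.3%.

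Fourth, the sentence could be parsed so that the phrase about other reasons also governs switching and rescue, which would leave rescued subjects in. The verb forms in the numerator and denominator paragraphs, such as "received any rescue medication (including BZDs) during the first 3 hours after the initiation of BRV treatment", make rescue a separate ground for exclusion. If the other meaning was intended, the text still needs correcting.

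The first three arguments stand and set the size of the point. None of the four removes the core: subjects with a defined outcome are treated as missing, and those with missing VEEG are not examined.

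**Conclusion.** The point holds in this limited form. SAP 8.2.3 does not do what its stated purpose and Protocol 13.7 call for. It deletes subjects who are non-responders by the plan's own definition, a step that can raise the responder rate but never lower it. The deletion of other-reason dropouts and the missing 3-hour limit in its opening paragraph make the net direction of the whole analysis uncertain, though the tendency is to favour BRV.

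In the illustration, the deletion adds about 5 points to the rate with 5 early rescues or switches (33.3% to 38.7%) and about 13 points with 10 (33.3% to 46.2%). These sizes rest on an assumed FAS of 36, 12 responders and the stated removals. The true shift depends on rescue and response counts that the documents do not give.

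The consequence is a mislabelled supporting table, with no change to the main analysis or to the comparison with historical controls. It should still be corrected, because as planned the effect of missing VEEG on the main efficacy variable will remain unknown.

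**What to change.** Rewrite SAP 8.2.3 as follows:

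- Keep subjects rescued or switched in the first 3 hours in the denominator as non-responders. Lack-of-efficacy dropouts already stay in and need no change.
- State one time window, the first 3 hours, in every paragraph of the section.
- Define missing as a response that cannot be determined because Baseline or 1-to-3-hour VEEG is insufficient, in a subject with no rescue, switch or lack-of-efficacy dropout in that window. Other-reason dropouts count as missing only if they meet this definition.
- Use all treated Confirmatory Cohort subjects as the denominator. Report the rate with its 95% CI twice: missing counted as non-responders, then as responders.
- If an analysis without rescued or switched subjects is still wanted, label it supplementary and not a missing-data sensitivity analysis.

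The cost is a change of SAP wording and one reprogrammed table. No additional data collection is needed.

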8.2.4 Derivations of the secondary efficacy variables

The following secondary efficacy variables are defined as follows:

- Proportion of subjects with at least 80% reduction in non-severe seizure burden from Baseline to 3 hours after the initial BRV treatment [*derivations*: see the definition of baseline non-severe seizure burden in [Section 8.1.2.1](#); reduction of at least 80% in non-severe seizure burden from baseline is defined as a $\geq 80\%$ difference between average per hour seizure burden at baseline (calculated over the 1-hour Baseline Period) and average per hour seizure burden calculated over 3 hours after the start of initial BRV treatment divided by the average per hour seizure burden at baseline and multiplied by 100. The numerator is defined as the number of subjects with the 80% reduction described above. The denominator is defined as the number of subjects in the FAS from Confirmatory Cohorts with baseline non-severe seizure burden.]
- Proportion of subjects with at least 50% reduction in severe seizure burden from Baseline to 3 hours after the initial BRV treatment [*derivations*: see the definition of baseline severe seizure burden in [Section 8.1.2.2](#); reduction of at least 50% in severe seizure burden from baseline is defined as a $\geq 50\%$ difference between average per hour seizure burden at baseline (calculated over the 1-hour Baseline Period) and average per hour seizure burden calculated over 3 hours after the start of initial BRV treatment divided by the average per hour seizure burden at baseline and multiplied by 100. The numerator is defined as the number of subjects with the 50% reduction described above. The denominator is defined as the number of subjects in the FAS from Confirmatory Cohorts with baseline severe seizure burden.]
- Absolute reduction in average seizure burden measured by continuous VEEG from Baseline to the end of the 96-hour Evaluation Period [*derivations*: see the definition of baseline seizure burden and of average per hour seizure burden in [Section 8.1](#), average per hour over 96-hour Evaluation Period seizure burden is calculated as the total seizure burden during the 96-hour Evaluation Period divided by 96, the number of hours in the Evaluation Period, average per hour seizure baseline seizure burden is calculated as the total seizure burden over 1-hour Baseline Period divided by 1. The **absolute reduction** in average per hour seizure burden is defined as the average per hour seizure burden at the end of the 96-hour Evaluation Period minus average per hour baseline seizure burden]

- Percentage reduction in average seizure burden measured by continuous VEEG from Baseline to the end of the 96-hour Evaluation Period [**derivations**: see the definition of baseline seizure burden and of average per hour seizure burden in [Section 8.1](#), average per hour over 96-hour Evaluation Period seizure burden is calculated as the total seizure burden during the 96-hour Evaluation Period divided by 96, the number of hours in the Evaluation Period, average per hour seizure baseline seizure burden is calculated as the total seizure burden over 1-hour Baseline Period divided by 1. The **percentage reduction** is defined as the absolute reduction in average per hour seizure burden divided by the average per hour baseline seizure burden and multiplied by 100.]
- Proportion of BRV responders during the 96-hour Evaluation Period (measured at the end of the 96-hour Evaluation Period) [**derivations**: see the definition of BRV responders for other than main efficacy variable in [Section 8.1](#), the post-baseline seizure burden will be evaluated during the last 1 hour of the 96-hour Evaluation Period, the denominator is defined as the number of subjects in the FAS from Confirmatory Cohorts.]
- Proportion of subjects who are seizure-free (100% reduction in seizure burden from Baseline, i.e. those subjects whose seizure burden disappeared) at 24 hours following the start of initial BRV treatment, categorized by subjects with non-severe or severe seizure burden at Baseline [**derivations**: the numerator is the number of subjects with 100% reduction in seizure burden from Baseline or no ENS during the last 2 hours of the 24-hour time period following the start of initial BRV treatment, see the definition of baseline seizure burden in [Section 8.1](#), the denominator is defined as the number of subjects in the FAS from Confirmatory Cohorts.]
- Time to reduction in seizure burden for BRV responders (defined as the first time point when BRV responder criteria are met) [**derivations**: the time to reduction in seizure burden is measured in hours, defined as the first time point (date and time) when BRV responder criteria are met minus the date and time of the first BRV dose, event is defined as response to BRV, subjects will be evaluated for response at the following time points: 3 hours, 4 hours, 5 hours, etc., 96 hours after the initial BRV dose. Response will be calculated referring to the last 1 hour prior to the time point. Non-responder for the analysis of other than main efficacy variable subjects defined in the [Section 8.1](#) are censored with time to censoring defined as the date and time of the event defining the non-responder status (drop out due to lack of BRV efficacy, switch over to another AED treatment, used >1 dose of rescue medication following the first 3 hours after initiation of BRV treatment) or date and time of the end of the Evaluation Period in case there are no events of response or non-response minus the date and time of first BRV dose; when the time is not collected, use HH:MM=23:59.]
- Seizure freedom at the end of the Down-Titration Period (Confirmatory Cohorts only) [**derivations**: defined as proportion of subjects who are seizure-free at the end of the Down-Titration Period, the numerator is the number of subjects with seizure-freedom defined as no ENS at the end of the Down-Titration Period, i.e. no ENS during 1 hour of VEEG, the denominator is defined as the number of subjects in the FAS from Confirmatory cohorts with VEEG data at the end of the Down-Titration Period.]
- Rate of at least 50% reduction in ENS frequency per hour from Baseline to the end of the 96-hour Evaluation Period [**derivations**: the numerator is defined as the number of subjects with the 50% reduction in ENS frequency, i.e. the difference between the average ENS frequency

per hour at Baseline and the average ENS frequency per hour over the 96-hour Evaluation Period divided by the average per hour Baseline ENS frequency and multiplied by 100 should be at least 50%, the denominator is defined as the number of subjects in the FAS from Confirmatory Cohorts. Average per hour ENS frequency at Baseline is calculated as the total number of ENS over 1-hour Baseline Period divided by 1; average per hour ENS frequency at the end of the 96-hour Evaluation Period is defined as the number of ENS over 96-hour Evaluation Period divided by 96.]

- Proportion of subjects who are seizure-free by time interval at 3 hours, at 3-hour intervals thereafter through 24 hours, and every 12 hours to 24 hours following the start of the initial BRV treatment [*derivations*: the numerator is defined as the number of subjects with no ENS or 100% reduction in seizure burden from Baseline to 3 hours after the first BRV dose and then with no seizure burden at 6, 9, 12, 15, 18, 21, 24, 36, 48, 60, 72, 84, 96 hours after the first BRV dose, the 2 hours of VEEG prior to the defined time point will be evaluated for seizure freedom/ENS absence; the denominator is defined as the number of subjects in the FAS from Confirmatory Cohorts, see the definition of reduction in seizure burden from Baseline in [Section 8.1](#).]
- Absolute difference in clinical seizures (annotated by central reader) at the end of the first 24-hour of the 96-hour Evaluation Period from Baseline for neonates with motor seizures at the time of inclusion [*derivations: absolute difference* is defined as the difference between the number of clinical seizures observed during the 1-hour Baseline Period and the number of post-baseline clinical seizures observed during the 1 hour prior to the end of the 24-hour Evaluation Period]
- Percent difference in clinical seizures (annotated by central reader) at the end of the first 24 hour of the 96-hour Evaluation Period from Baseline for neonates with motor seizures at The Time of Inclusion [*Derivations: Percent Difference* is Defined as the Absolute Difference in Clinical Seizures (Defined Above) Divided by the Number of Clinical Seizures During The Baseline Period and Multiplied by 100.]

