4.2.1 Secondary efficacy variables

The main secondary efficacy variable is as follows:

- Proportion of responders to BRV treatment from Baseline to 3 hours after the initial BRV dose

A BRV responder is defined as a subject who achieves the following reduction in seizure burden (ENS in minutes per hour) without need for rescue medication, compared to the seizure burden measured during the Baseline Period immediately prior to BRV administration, evaluated for a 2-hour period starting 1 hour after the start of initial BRV treatment:

- At least 80% reduction in nonsevere seizure burden

(Nonsevere seizure burden is defined as $\leq 50\%$ seizure activity on VEEG in all 30-minute timespans)

OR

- At least 50% reduction in severe seizure burden

(Severe seizure burden is defined as $> 50\%$ seizure activity on VEEG in any 30-minute timespan). Timespans of 30 minutes refer to the following intervals within the 2-hour period: 0 to ≤ 30 minutes, > 30 to ≤ 60 minutes, > 60 to ≤ 90 minutes, and > 90 to ≤ 120 minutes.

For this study, an ENS is defined as an EEG seizure lasting for at least 10 seconds on VEEG. Baseline seizure burden is defined as seizure burden measured on the continuous VEEG (total ENS in minutes per hour) during a period of up to 1 hour immediately prior to the first administration of study drug.

In addition, the secondary efficacy variables will include:

- Proportion of subjects with at least 80% reduction in nonsevere seizure burden from Baseline to 3 hours after the initial BRV treatment
- Proportion of subjects with at least 50% reduction in severe seizure burden from Baseline to 3 hours after the initial BRV treatment
- Absolute reduction in average seizure burden measured by continuous VEEG from Baseline to the end of the 96-hour Evaluation Period
- Percent reduction in average seizure burden measured by continuous VEEG from Baseline to the end of the 96-hour Evaluation Period
- Proportion of BRV responders at the end of the 96-hour Evaluation Period
- Proportion of subjects who are seizure-free (100% reduction in seizure burden from Baseline) at 24 hours following the start of initial BRV treatment, categorized by subjects with nonsevere or severe seizure burden at Baseline

- Time to reduction in seizure burden for BRV responders (defined as the first timepoint when BRV responder criteria are met)
- Seizure freedom at the end of the Down-Titration Period

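### SAP 8.2.4 derives the severity-specific 80% and 50% response variables over hours 0 to 3 with no early-rescue rule, while the main responder variable uses hours 1 to 3 and counts early rescue as non-response, so the severity results do not break down the main rate

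*SAP*

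**What the plan says.** The main variable: "The main secondary efficacy variable is the proportion of responders to BRV treatment from Baseline to 3 hours after the initial BRV dose" (SAP 8.2.1). For its numerator, the same section says "The numerator is the number of BRV responders for main secondary efficacy variable defined in" Section 8.1. There, SAP 8.1.1 requires a reduction of at least 80% (non-severe) or at least 50% (severe), "evaluated for a 2-hour period starting 1 hour after the start of initial BRV treatment". Protocol 4.2.1, 10.1 and 13.5.1 give the same window. SAP 8.1.1 also classes as non-responders babies who drop out for lack of efficacy, switch to another AED or receive rescue during the first 3 hours.

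The two severity variables: Protocol 4.2.1 lists "Proportion of subjects with at least 80% reduction in nonsevere seizure burden from Baseline to 3 hours after the initial BRV treatment" and a matching 50% variable for severe burden. It gives neither an averaging window of its own. SAP 8.2.4 supplies one. Both derivations compare Baseline with "average per hour seizure burden calculated over 3 hours after the start of initial BRV treatment". Each numerator counts babies with the required reduction and makes no reference to responder status or rescue. The denominators are separate: "The denominator is defined as the number of subjects in the FAS from Confirmatory Cohorts with baseline non-severe seizure burden" and "The denominator is defined as the number of subjects in the FAS from Confirmatory Cohorts with baseline severe seizure burden".

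SAP 8.1.5 gives the percent-change formula but leaves the post-dose period open: "seizure burden calculated over given period of time after the start of initial BRV treatment divided by the average per hour seizure burden at baseline". SAP 3.10, the table of changes to protocol-defined analyses, contains only the regrouping of seizure causes.

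**The concern.** Three variables share the 80% and 50% thresholds, the Baseline severity classes and an end point of 3 hours. A reader of the results will naturally take the two severity proportions as the breakdown of the main responder rate. Because the window and the rescue handling differ, they are not.

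The first hour is the one in which a difference is most plausible. It contains the infusion of about 15 minutes, and the main variable leaves it out.

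Evaluating efficacy in severe and non-severe burden is a stated secondary objective (Protocol 3.2, SAP 2.1.2). If the severity-specific results and the main rate point in different directions, the report cannot say whether the cause is severity, the window or rescue.

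**Working it through.** The documents give no figure to reproduce here: there is no sample size calculation, no power and no test (SAP 2.4 and 4.5). The check applies the SAP 8.1.5 formula to both windows.

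**Formula.** Percent reduction = 100 × (Baseline − post-dose) / Baseline, in minutes of seizure per hour. Let r1 be the reduction in hour 0–1 and r2 the reduction over hours 1–3. With complete recording, the 0–3 h reduction is (r1 + 2 × r2) / 3.

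**When a main responder misses its severity variable.**
- Non-severe (r2 ≥ 80): missed if r1 < 240 − 2 × r2. At r2 = 100 this is r1 < 40, a first-hour burden above 60% of Baseline. At r2 = 80 it is r1 < 80, a first-hour burden above 20% of Baseline.
- Severe (r2 ≥ 50): missed if r1 < 150 − 2 × r2. At r2 = 60 this is r1 < 30. At r2 = 75 it is r1 < 0.
- If first-hour burden equals Baseline (r1 = 0), the 0–3 h reduction is two thirds of r2. A non-severe baby then reaches at most 66.7% and cannot pass. A severe baby needs r2 ≥ 75.

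**Worked cases.** The hourly burdens (min/h) are assumed for illustration.

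| Baseline class | Baseline | Hours 0–1, 1–2, 2–3 | 1–3 h reduction | Main variable | 0–3 h reduction | Severity variable |
|---|---|---|---|---|---|---|
| Non-severe | 12 | 12, 0, 0 | 100% | met | 66.7% | not met |
| Non-severe | 12 | 6, 1, 1 | 91.7% | met | 77.8% | not met |
| Non-severe | 12 | 0, 3, 3 | 75.0% | not met | 83.3% | met |
| Severe | 36 | 36, 12, 12 | 66.7% | met | 44.4% | not met |
| Severe | 36 | 36, 0, 0 | 100% | met | 66.7% | met |
| Severe | 36 | 0, 20, 20 | 44.4% | not met | 63.0% | met |

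Two cases near the thresholds:
- Non-severe, first hour at 70% of Baseline, then seizure-free: 1 − 0.7/3 = 76.7%, not met.
- Severe, first hour at 80% of Baseline, then at 40%: 1 − (0.8 + 2 × 0.4)/3 = 46.7%, not met, although r2 = 60.

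**Rescue.** Under SAP 8.1.1 a baby rescued at, say, 1.5 hours is a main non-responder whatever its burden. Under SAP 8.2.4 the same baby counts as a success if the burden falls far enough. SAP 4.2.3 does not close the gap, because its rescue rule concerns use after the first 3 hours.

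**Scale.** If all 36 planned Confirmatory subjects entered the Full Analysis Set, one reclassified baby would be 1/36 = 2.8 percentage points overall, and more within a severity class.

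**The case against.** The best defence is that Protocol 4.2.1 introduces these as further secondary variables and attaches the 2-hour window only to the responder definition. Neither document promises that they add up to the main count. Read literally, a change from Baseline to 3 hours covers hours 0 to 3, just as SAP 8.2.4 averages the 96-hour variables over all 96 hours. SAP 8.3.1 also plans a 0-to-3-hour responder proportion, so a matching total exists apart from rescue and dropout handling. On that view, SAP 3.10 omits nothing.

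This shows that 0 to 3 hours is a possible reading, not that it is a clear one. For seizure freedom at 3 hours, the same SAP section looks at the 2 hours before the time point. The baby with burdens 12, 0, 0 would thus be seizure-free at 3 hours and a main responder, yet would fail the 80% variable. The defence also leaves the missing early-rescue rule unanswered.

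Three stronger inferences are tempting, and the documents do not support them:
- That a baby can fail both severity variables. The denominators are disjoint, so each baby is assessed for one only.
- That the severity variables are uniformly stricter. The 0, 3, 3 case goes the other way, and the absence of a rescue rule makes them more lenient on that point.
- That the 0-to-3-hour versions could be dropped without loss. The 0-to-3-hour variables in SAP 8.3.1 are not split by baseline severity; SAP 4.8 and Section 8 specify subgroups only by seizure cause and hypothermia.

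**Conclusion.** The mismatch stands: two windows and two treatments of early rescue apply to variables with the same thresholds and time label. Under the current derivations, the severity numerators need not sum to the main responder count, and the discrepancy can go either way. The change should be made before analysis, but it is not critical.

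A reader might infer that the main responder rate or its comparison with historical controls is compromised. It is not: both rest on SAP 8.1.1, which agrees with the protocol on the window. No error rate or power is at stake, because all analyses are descriptive (SAP 4.5).

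The arithmetic assumes complete recording over the 3 hours. The first-hour burdens are illustrative, and how often babies would be classified differently cannot be determined from the documents.

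**What to change.** In SAP 8.2.4, derive both severity variables over hours 1 to 3 and apply the same first-3-hour rescue, switch and dropout rule as SAP 8.1.1. With the Baseline severity classes unchanged, the two numerators then sum to the main responder count and the two denominators to the Full Analysis Set of the Confirmatory Cohorts. Keep the 0-to-3-hour versions, split by baseline severity, as supportive results under SAP 8.3.1.

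The cost is SAP wording, one extra supportive table and a departure from the literal 0-to-3-hour reading of the label. If the sponsor prefers 0 to 3 hours, the SAP should say so, list it in 3.10, add the main responder proportion by baseline severity and state that the severity variables do not partition the main responders.

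A separate conflict needs its own reconciliation. For secondary variables other than the main one, Protocol 10.1 counts babies given rescue after the first 3 hours as responders, whereas Protocol 13.5.1 requires no such rescue for responder status.
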